### 5.1. Inclusion Criteria

*Patients can be enrolled into this study if all of the following criteria are met at screening visit:*

1. Hospitalized patient with clinical diagnosis of SARS-CoV-2 virus infection per World Health Organization criteria including positive nucleic acid test of any specimen (e.g., respiratory, blood, or other bodily fluid) within 2 weeks prior to screening.
2. Symptoms suggestive of severe systemic illness with COVID-19, which could include any of the following symptoms: fever, cough, sore throat, malaise, headache, muscle pain, gastrointestinal symptoms, or shortness of breath at rest, or respiratory distress.
3. Clinical signs indicative of severe systemic illness with COVID-19, which could include any of the following clinical signs: respiratory rate  $\geq 30$  per minutes, heart rate  $\geq 125$  per minute,  $\text{SpO}_2 \leq 93\%$  on room air,  $\text{PaO}_2/\text{FiO}_2$  ratio  $< 300$  mmHg, or lung infiltration  $>50\%$  on chest X-ray imaging.
4. Patients with plasma CRP level  $>50$  mg/L or 4x upper limit of normal range at screening.
5. Men or women  $\geq 18$  but  $\leq 80$  years of age at the time of signing the informed consent form.
6. Use of home oxygen is allowed
7. Patient is able to understand the purpose and risks of the study and provide signed and dated informed consent or have a legal representative provide consent and authorization to use protected health information (in accordance with national and local patient privacy regulations).
8. Patient is able to swallow tablets or receive delivery of oral suspension via a nasogastric tube.
9. Patient agrees not to participate in another interventional study after signing the informed consent form and until the end of study (EoS) visit has been completed.

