## Appendix 2: WHO Ordinal Scale

The WHO ordinal scale is a 10-level ordered categorical scale developed by a special committee at WHO to measure illness severity over time. The scale could be a measure of patients' clinical status at a particular time point after enrollment. A 2-point reduction on the score is considered as clinical improvement

Patient State	Descriptor	Score
Uninfected	Uninfected; no viral RNA detected	0
Ambulatory Mild Disease	Asymptomatic; viral RNA detected	1
	Symptomatic; Independent	2
	Symptomatic; Assistance needed	3
Hospitalized: Moderate disease	Hospitalized; no oxygen therapy	4
	Hospitalized; oxygen by mask or nasal prongs	5
	Hospitalized; Oxygen by NIV or High flow	6
Hospitalized: Severe disease	Intubation & mechanical ventilation, $pO_2/FIO_2 \geq 150$ or $SpO_2/FIO_2 \geq 200$	7
	Mechanical ventilation $pO_2/FIO_2 < 150$ ( $SpO_2/FIO_2 < 200$ ) or vasopressors	8
	Mechanical ventilation $pO_2/FIO_2 < 150$ and vasopressors, dialysis, or ECMO	9
Death	Dead	10

Sironax, Ltd

SIR365-US-101 Clinical Study Report

Product Name: SIR1-365

Study Number: SIR365-US-101

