### **Appendix 3: Clinical Laboratory Tests To be Performed at Local Laboratory**

- The tests detailed in the [table](#) below will be performed at local laboratories. Investigators must document their review of each laboratory safety report.
- All other protocol-required tests will be analyzed by a central laboratory.
- Additional tests may be performed at any time during the study as determined necessary by the Investigator or required by local regulations.
- Protocol-specific requirements for inclusion or exclusion of patients are detailed in the protocol.

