Informed consent	X									
Medical history	X									
Demographics	X									
Physical examinations	X ⁴								X	
Vital signs ⁵	X	X	X	X	X	X	X	X		X

12-lead ECG	X	X ⁶		X		X		X	X
Blood samples for routine lab tests including CRP and ferritin ⁷	X	X	X	X	X	X	X	X	X
Blood samples for coagulopathy and cardiac panels ⁸		X	X	X		X		X	X
Urine sample for urinalysis	X	X	X	X		X		X	X
Serum serology and pregnancy tests for screening	X								
Inclusion and exclusion	X								
Randomization		X							
Treatment		X	X	X	X	X	X	X	
Oxygen use and saturation (pulse oximetry)	X	X	X	X	X	X	X	X	X
PaO ₂ /FiO ₂ ratio	X	X		X				X	
WHO ordinal scale		X		X				X ¹³	X
Blood sample for cytokine/chemokine panels and CV biomarkers ⁹		X		X				X	
Blood sample for PK analysis and pRIP1/pMLKL assay ¹⁰		X		X				X	
Urine sample for NGAL and KM-1 assay ¹¹		X		X				X	
AE and ConMed	X	X	X	X	X	X	X	X	X

1. Enrollment and Baseline. Screening and Baseline visits can be combined. ECG, laboratory test and other test results taken within 24 hours prior to consent will be used as Baselines.
2. End of Treatment (EOT) or early discharge.
3. End of the study (EOS) or early discontinuation.
4. For enrolled patients, physical examination obtained at screening will be the Baseline. Weight and height will be measured at screening.
5. Vital signs will be taken before the 1st dose on Day 1 as Baseline, and within 3 hours before the 2nd dose on other days.
6. Three ECGs with 1-3 min interval before the 1st dose on Day 1 only, and the means of the 3 ECGs will be used as Baselines. ECGs will be done within 3 hours before the 2nd dose on other days. Local ECG machine will be used in this study.
7. Routine laboratory tests before the 2nd dose will be done daily at local labs. CRP and ferritin tests will be done on Days 1, 3, 7, 10 and 14.
8. Coagulopathy panel including D-dimer, fibrinogen, PT, PTT and INR, and cardiac function panel including NT-proBNP (or BNP) and high-sensitivity cardiac troponin will be done on Days 1, 3, 7, 10 and 14 at local labs with samples collected before the 2nd dose.
9. One blood sample collected before the 1st dose on Day 1 and before the 2nd dose on Days 7 and 14 for cytokine/chemokine panels and CV biomarker assays to be conducted at a central lab

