10. One blood sample will be collected from each patient within 30 min before and 2 hours (± 5 min) after the 1st dose on Day 1, respectively. On Days 7 and 14, one blood sample will be collected within 30 min before and 2 hours (± 5 min) after the 2nd dose, respectively. Each plasma sample will be divided into 4 parts, 2 for PK analysis and 2 for plasma pRIP1/pMLKL assay conducted at a central lab. PBMC preparation will be done at the sites with necessary equipment according to the laboratory manual for pRIP1/pMLKL assay.
11. About 10 mL of urine sample will be collected before dosing on Day 1, and in the morning on Days 7 and 14 for NGAL and KIM-1 assay to be conducted at a central lab
12. If the patients are discharged from the hospital before Day 14, all the assessments planned for Day 14 should be carried out before discharge. Study drugs will not be administered in early discharged patients. It is preferred that the follow-up visit is in person to obtain safety laboratory tests. However, infection control or other restrictions may limit the ability of the patients to return to the clinic. In this case, the follow-up visit may be conducted by phone and only safety data will be obtained. If a patient is still hospitalized after Day 14, no study drug will be administered after the last dose on Day 14.
13. When completing the WHO Ordinal Scale at Day 14/ EOT, if the subject has received physician orders to be discharged from the hospital, the score should be a 3 or less (*no longer hospitalized*).

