The distribution of outcomes on the ordinal scale will also be plotted using stacked bar charts representing the proportion of patients in each category (uninfected, ambulatory mild disease, hospitalized: moderate disease, hospitalized: severe disease and death), by treatment group over time. A second plot will be produced, similar to what is described above, summarizing the results at Day 7 (assessments taking place on study day 7), Day 14 (assessments taking place on study day 14) and Day 28 (assessments taking place on study day 28). For any patients with missing Day 7 results, the Day 7 results will be imputed using the last value reported prior to study day 7. Similarly, Day 14 missing observations will be imputed with the last available assessment that took place after study day 7 and prior to study day 14. Day 28 missing observations will be imputed with the last available assessment that took place after study day 14.

The mean absolute values and mean absolute change from Baseline up to Day 14, using the actual study day for Day14/EOT assessments, will be plotted per treatment group using line graphs.

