13.1.4.1 Time to clinical improvement

Time to clinical improvement is defined as the number of days between the date of first study drug administration and the first date a patient achieves a 2-point reduction on the WHO ordinal scale.

Time to clinical improvement will be analyzed using a Cox proportional hazards model to estimate the hazard ratio and corresponding 95% CI for SIR1-365 dose vs placebo.

The proportional hazard regression model will include a single term for treatment.

- Death prior to clinical improvement will be handled as a competing risk event.
- Patients that do not show any clinical improvement over the assessment period will be censored at the date of last assessment.
- Patients with no post-baseline assessment value will be censored at Day 1.

The hazard ratio estimation of the event of interest (clinical improvement) will be derived from a cumulative incidence function. The Kaplan Meier estimate of median time to event will also be presented for each treatment group.

Table 12.1.4 Categories for WHO Ordinal Scale

Patient State	Descriptor	Score
Uninfected	Uninfected; no viral RNA detected	0
Ambulatory Mild Disease	Asymptomatic; viral RNA detected	1
	Symptomatic; Independent	2
	Symptomatic; Assistance needed	3
Hospitalized: Moderate disease	Hospitalized; no oxygen therapy	4
	Hospitalized; oxygen by mask or nasal prongs	5
Hospitalized: Severe disease	Hospitalized; Oxygen by NIV or High flow	6
	Intubation & mechanical ventilation, $pO_2/FIO_2 \geq 150$ or $SpO_2/FIO_2 \geq 200$	7
	Mechanical ventilation $pO_2/FIO_2 < 150$ ($SpO_2/FIO_2 < 200$) or vasopressors	8

	Mechanical ventilation $pO_2/FIO_2 < 150$ and vasopressors, dialysis or ECMO	9
Death	Dead	10

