Appendix 2: Clinical Laboratory Tests to be Performed at Local Laboratory

Routine Clinical Laboratory Tests

Hematology	Clinical Chemistry		Urinalysis
Hemoglobin (Hgb)	Glucose	C-Reactive Protein (CRP)	pH
Hematocrit (Hct)	Albumin	Ferritin	Specific gravity
Red blood cell count	Total protein	Lactic dehydrogenase (LDH)	Protein
White blood cell count with differential	Bicarbonate	Urate	Glucose
Platelet count	Phosphate	Urea	Ketones
	Sodium	Creatinine	Bilirubin
	Potassium	Total bilirubin (TBL)	Blood
	Chloride	Alkaline phosphatase (ALP)	Nitrites
	Calcium	Aspartate transaminase (AST)	Leukocytes
	Total cholesterol (TC)	Alanine transaminase (ALT)	Urobilinogen
	Low-density lipoprotein cholesterol (LDL-C)	Gamma-glutamyl transferase (GGT)	Microscopic analysis
	Triglyceride (TG)		

Other Clinical Laboratory Tests

Serology Tests for Screening	Coagulopathy Panel	Cardiac Function Panel
Human immunodeficiency virus (HIV)	D-dimer	High-sensitivity cardiac troponin
Hepatitis B surface antigen (HBsAg)	Fibrinogen	NT-proBNP or BNP
Hepatitis C virus (HCV)	Prothrombin time (PT)	
Pregnancy test	Partial thromboplastin time (PTT)	
	International normalized ratio (INR)	

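### For a symptom-free discharged patient, WHO scores 0 and 1 differ only by a viral RNA result that the plan never schedules, so several secondary WHO-scale summaries partly reflect local re-testing

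*SAP*

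**What the plan says.** The two lowest levels of the scale are worded by RNA status. Score 0 is "Uninfected; no viral RNA detected" (SAP 13.1.4.1, Table 12.1.4) and score 1 is "Asymptomatic; viral RNA detected" (Protocol Appendix 2, with the same wording in the SAP table). Scores 2 and 3 are for symptomatic patients out of hospital and need no RNA result.

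The only RNA result that the documents require is the entry criterion in Protocol 5.1, "including positive nucleic acid test of any specimen (e.g., respiratory, blood, or other bodily fluid) within 2 weeks prior to screening". The scale is scored at Baseline and on Days 7, 14 and 28. The one scoring instruction, footnote 13 to SAP Table 5.2, reads "if the subject has received physician orders to be discharged from the hospital, the score should be a 3 or less". It applies at Day 14/EOT and does not say how to choose among 0 to 3.

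The SAP uses the numeric score in several places:
- 13.1.4 summarises change and percentage change as continuous variables and plots mean values and mean changes.
- 13.1 says that mean changes in continuous measures will be compared between groups on an exploratory basis.
- 13.2 rank-correlates the change with baseline biomarkers.
- 12.3 repeats the WHO analysis for the USA, Mexico and Pakistan.
- The stacked bars in 13.1.4 use the categories "uninfected, ambulatory mild disease, hospitalized: moderate disease, hospitalized: severe disease and death", so score 0 has its own bar.

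**The concern.** A patient who has gone home without symptoms belongs at 0 or at 1, and only an RNA result decides which. If the protocol does not collect that result, the recorded score depends on whether a hospital re-tested for its own reasons, or on what the rater assumed. The uninfected bar would then show testing practice as much as recovery. The same applies, by up to one point per affected patient, to every summary that treats the score as a number. SAP 6 says that the trial's estimates are meant for planning later studies, so an artefact in a mean or a bar could be carried forward.

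**Working it through.** The plan gives no figure to reproduce here: SAP 6 says that the sample size was not calculated. The check has two parts, a search for an RNA test and arithmetic on the scale.

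**1. Is RNA measured after entry?** SAP Table 5.2 was used because some row labels in the protocol's schedule are blacked out.
- Table 5.2 has no SARS-CoV-2 RNA row. The row "Serum serology and pregnancy tests for screening" is marked at screening only.
- In SAP Appendix 2, the column "Serology Tests for Screening" lists HIV, hepatitis B surface antigen, hepatitis C and pregnancy.
- The visit lists in Protocol 9.1 to 9.9, Protocol Appendix 3 and the PK/PD plan name no RNA test.
- Protocol Appendix 3 does allow that "Additional tests may be performed at any time during the study as determined necessary by the Investigator". Discretionary local re-testing is therefore the only evident source of a later RNA result. This is an inference, since the documents do not mention re-testing.

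**2. Effect on one patient.** Eligible patients are hospitalised and not mechanically ventilated, so baseline scores of 4, 5 and 6 were taken. Change = score − baseline. Percentage change = 100 × change / baseline. Improvement = a reduction of at least 2 points.

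| Baseline | Change if 0 / if 1 | % change if 0 / if 1 | Improved if 0 / if 1 |
|---|---|---|---|
| 4 | −4 / −3 | −100 / −75 | yes / yes |
| 5 | −5 / −4 | −100 / −80 | yes / yes |
| 6 | −6 / −5 | −100 / −83.3 | yes / yes |

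The choice moves the change by 1 point and never alters improvement status. It therefore does not alter time to improvement either.

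**3. Effect on one arm.** Let r of 30 patients be discharged and symptom-free, and let a share t of them be re-tested and RNA-negative. Uninfected bar = 100 × r × t / 30. Shift in mean score = −r × t / 30. The values of r are assumptions.

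| r of 30 | Bar, t = 0 to 1 | Shift in mean, t = 0 to 1 |
|---|---|---|
| 9 (30%) | 0% to 30% | 0 to −0.30 |
| 15 (50%) | 0% to 50% | 0 to −0.50 |
| 24 (80%) | 0% to 80% | 0 to −0.80 |

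These ranges compare no re-testing with universal negative re-testing. They are not differences between arms.

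**4. Effect between arms.** With equal recovery and a re-testing share that differs by d between arms, the artefact in the mean difference is r × d / 30. For an assumed d of 0.25:
- 9 × 0.25 / 30 = 0.075 points (7.5 percentage points of bar)
- 15 × 0.25 / 30 = 0.125 points (12.5 percentage points)
- 24 × 0.25 / 30 = 0.20 points (20 percentage points)

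For comparison, the 95% half-width for a mean difference at 30 per arm is 1.96 × SD × √(2/30). That is 0.76, 1.01 and 1.27 points for assumed SDs of 1.5, 2 and 2.5. The largest artefact above is about a quarter of the narrowest half-width (0.20 / 0.76 = 0.26).

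**5. Effect between countries.** Blinding does not even out practice across countries. If one country re-tested every symptom-free patient with a negative result and another re-tested none, their mean scores would differ by 0.30, 0.50 or 0.80 points at the recovery shares in step 3, with identical clinical outcomes. Within a country, the treatment contrast moves only if recovery or re-testing differs between arms.

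**The case against.** The strongest reply is that little rests on this distinction. The primary outcome is treatment-emergent adverse events. The WHO score has no model of its own, its between-group tests are exploratory, and the two WHO results closest to a conclusion, the 2-point improvement proportion and time to improvement, do not depend on 0 versus 1. All of this stands and limits the point to secondary and descriptive output.

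A reader might infer that the WHO comparison is biased towards one arm. The documents do not support that. Treatment is randomised and double-blind with matching tablets, and nothing suggests that re-testing would follow allocation. The 25-point imbalance in the working is only illustrative.

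A reader might also infer that most recovered patients are affected. The documents give no recovery rate. Discharged patients with residual symptoms score 2 or 3 without an RNA result, early-discharge scores are taken before the patient leaves hospital, and a Day 28 visit by phone collects safety data only. The share of affected patients is unknown.

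Finally, the annotated eCRF that the SAP cites is not available here and may hold a scoring convention. That could make the scoring uniform, but it could not supply an RNA result that nobody is asked to obtain. The uninfected bar would still count only patients who happened to be re-tested.

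**Conclusion.** The point holds within limits. After entry, scores 0 and 1 cannot be separated from protocol data, yet the SAP analyses the difference between them and displays score 0 as its own category. The outputs affected are the continuous and percentage-change summaries and plots, the Spearman correlations, the by-country WHO tables and the uninfected bar. The size is up to 1 point per symptom-free discharged patient. How far this moves a mean or a bar depends on assumed recovery and re-testing shares. The harm is mainly noise and site or country artefact.

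A neighbouring ambiguity remains. Score 0 does not mention symptoms, so an RNA-negative patient with residual symptoms might be given 0, 2 or 3. At baseline 4, a 3 rather than a 0 or 2 would change improvement status. That is a separate matter from 0 versus 1, and pooling those two scores does not settle it for the numeric summaries.

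**What to change.** Change SAP 13.1.4, 12.3 and 13.2 only, before unblinding:
- Pool scores 0 and 1 into one analysis level with value 1 for change and percentage change, the correlations and the country summaries. The shift r × t / 30 then becomes zero.
- Merge the uninfected bar with the ambulatory one under a label such as 'not hospitalised (score 0–3)'.
- Keep the score as recorded by the site in the listings.

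Do not tell sites to record 1 for every symptom-free discharged patient. That would attach a false descriptor to patients known to be RNA-negative, and editing the protocol's scale or footnote would need an amendment with IRB approval (Protocol 13). No RNA test needs to be added.

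The cost is a few SAP sentences and a chart legend, plus a line in SAP 15, which currently reports no changes to the protocol's analyses. The sample size, the improvement proportion and time to improvement are unchanged. The small downside is that the lowest level of the scale is no longer shown separately.

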13.1.5 Days of hospitalization

Days of hospitalization after treatment will be determined using the ‘Study Drug Administration’ and ‘Hospitalization Details’ eCRFs. The date and time (in format 23:59) of 1st dose of study drug and discharge will be collected.

Duration of hospitalization after treatment up through 14 days will be calculated as

- Duration of hospitalization after treatment (days) = (Date and time of discharge – Date and time of 1st dose of study drug)/60/24

Missing discharge times will be assumed to be ‘23:59’ in order to calculate the maximum duration of time hospitalized. In the event a patient is hospitalized more than 14 days, 14 days will be used for analysis.

For patients that died within the first 14 days while hospitalized, the duration of hospitalization will be imputed as 14 days in order not to underestimate the number of days of hospitalization. In the unlikely event a patient dies within 14 days but subsequent to discharge, the number of days hospitalized will be 14 minus the number of days from discharge to death.

For patients with multiple hospitalizations in the first 14 days, the sum of all intervals will be calculated for analysis.

Duration of hospitalization after treatment as a continuous variable will be summarized descriptively by treatment and analyzed using a 1-way ANOVA model with a single term for treatment.

A similar analysis will be done for the total duration of hospitalization:

- Total duration of hospitalization (days) = (Date and time of discharge – Date and time of admission)/60/24

Missing admission times will be assumed to be ‘00:00’ and missing discharge times will be assumed to be ‘23:59’ in order to calculate the maximum duration of time hospitalized.

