**Clinical Efficacy Endpoints:**

- Change from Baseline to Day 7 and Day 14 in PaO2/FiO2 ratio
- Time to improvement of oxygenation defined as oxygen saturation (pulse oximetry)  $>93\%$  and increased  $\geq 1\%$  from Baseline breathing only room air in the 48 hours preceding the measurement during the study (Baseline to Day 28)
- Number of days without oxygen use during the study (Baseline to Day 28)
- Change from Baseline to Days 7, 14 and 28 in the score of the WHO ordinal scale
- Proportion (%) of patients with clinical improvement defined as a reduction of 2 points in the WHO ordinal scale during the study (Baseline to Day 28).
- Number of days hospitalized during the study (Baseline to Day 28)
- Proportion (%) of patients free of respiratory failure during the study (Baseline to Day 28)

- All-cause mortality rate during the study (Baseline to Day 28)

Changes in clinical efficacy endpoints in patient populations with different Baseline levels of inflammatory biomarkers to assess the correlation of biomarker profile to clinical efficacy outcomes

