***Days of hospitalization***

Days of hospitalization as a continuous variable will be summarized by visit and treatment. The definition of a “day”, such as calendar day versus a 24 hours period, will be defined in the SAP.

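### Days hospitalized is defined to Day 28, but SAP 13.1.5 counts post-dose stay only to 14 days, and Section 15 declares no change

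*SAP*

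**What the plan says.** The protocol synopsis lists the secondary efficacy endpoint as "Number of days hospitalized during the study (Baseline to Day 28". The same Day 28 window appears in Protocol Section 4 and in SAP Sections 4 and 12.1.

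SAP 13.1.5 derives something else:

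- Window: "Duration of hospitalization after treatment up through 14 days will be calculated as" discharge minus first dose.
- Cap: "In the event a patient is hospitalized more than 14 days, 14 days will be used for analysis".
- Readmissions: "For patients with multiple hospitalizations in the first 14 days, the sum of all intervals will be calculated for analysis".
- Deaths: an in-hospital death in the first 14 days is scored as 14. For a death within 14 days but after discharge, "the number of days hospitalized will be 14 minus the number of days from discharge to death".

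The section then adds a second variable: "A similar analysis will be done for the total duration of hospitalization", running from admission to discharge. Both are analysed by one-way ANOVA with treatment as the only term.

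For this endpoint, Protocol 10.3.1 leaves to the SAP what counts as a day, "such as calendar day versus a 24 hours period, will be defined in the SAP". Protocol 10.3 also leaves missing-data rules to the SAP. SAP Section 15 states that nothing specified in the protocol was changed.

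**The concern.** The endpoint covers 28 days and the main derivation covers 14. If the SAP is followed as written, the clinical study report will give a 14-day quantity where the protocol promises a 28-day one, with nothing in Section 15 to tell the reader.

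The estimate itself is what matters here. The sample size is justified partly by the estimates of treatment differences it gives for planning later studies, and a difference in days over 14 days is not the same number as one over 28. In the post-dose variable, any separation between arms after Day 14 cannot be seen.

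**Working it through.** **1. Comparing the passages.** There is no stated power or effect figure for this endpoint to reproduce; the sample size is explicitly not power-based.

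| | Stated endpoint | 13.1.5 post-dose stay | 13.1.5 total duration |
|---|---|---|---|
| Start | Baseline | First dose | Admission |
| End | Day 28 | 14 days | Discharge, no limit stated |
| Readmissions | Within the window, by implication | First 14 days only | Not stated |
| Cap and death rules | Not stated | 14 days | Not stated |

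Total duration starts before Baseline because eligibility requires a "Hospitalized patient with clinical diagnosis of SARS-CoV-2 virus infection". So neither column on the right is the stated endpoint. The plan itself foresees patients still in hospital after Day 14 (Protocol 3.1, SAP Section 5).

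The neighbouring endpoint is handled differently. SAP 13.1.3 analyses days without oxygen through Day 28 and then repeats the analysis to Day 14, with a table for each. Hospitalization has Table 14.2.5.1 and a completer table, 14.2.5.2. Neither title names Day 28, and the completer analysis (SAP 12.3) repeats 13.1.5 and so inherits the cap.

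There is also a gap for patients never dosed. Efficacy is analysed in the ITT set, but 13.1.5 starts the clock at first dose and gives no start for an untreated patient. SAP 13.1.3 uses the randomization date.

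**2. Effect of the rule itself.** min(stay, 14) turns 16, 20, 25 and 28 days all into 14.

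**3. Size, under assumptions.** Assume log-normal stay after first dose with median m and log-scale SD s. With c the cap and z = ln(c/m)/s,

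E[min(stay, c)] = m·exp(s²/2)·Φ(z − s) + c·[1 − Φ(z)].

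Example, medians 14 and 10, s = 0.8:

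- c = 14, median 14: 19.28 × 0.2119 + 14 × 0.5000 = 11.09
- c = 14, median 10: 13.77 × 0.3522 + 14 × 0.3370 = 9.57. Difference 1.52 days.
- c = 28, median 14: 19.28 × 0.5265 + 28 × 0.1931 = 15.56
- c = 28, median 10: 13.77 × 0.6869 + 28 × 0.0990 = 12.23. Difference 3.33 days.
- Ratio 1.52/3.33 = 0.46.

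Ratio of the 14-day to the 28-day difference, with no deaths or equal death rates:

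| SD(log) | 7/5 | 10/8 | 14/10 | 18/14 |
|---|---|---|---|---|
| 0.5 | 0.89 | 0.68 | 0.49 | 0.31 |
| 0.8 | 0.69 | 0.55 | 0.46 | 0.37 |
| 1.0 | 0.62 | 0.52 | 0.46 | 0.39 |

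The share of stays cut by the cap runs from 2% (median 5, SD 0.5) to 69% (median 18, SD 0.5).

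**4. Unequal in-hospital deaths, scored at the cap.**

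- 20% in the longer-stay arm, 10% in the other: the ratio is 0.26 to 0.60.
- 10% in the longer-stay arm, 20% in the other: the ratio is 0.42 to 0.70 for 14/10 and 18/14. For 7/5 and 10/8 the 14-day difference becomes the larger one, 0.30 to 0.96 days against −0.21 to 0.06 over 28 days.

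**5. Precision.** Without deaths, the standardised effect (14-day minus 28-day) changes by −0.08 to +0.03. Over death rates of 20/10, 10/20, 10/10 and 20/20% it changes by −0.10 to +0.27, mostly in favour of 14 days. A separate simulation without deaths (control medians 7, 10 and 14, active median 0.75 times control, SD 0.5 and 0.8) gave power at 30 per arm of 0.24 to 0.59 with the 14-day cap and 0.25 to 0.58 with the 28-day cap.

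**The case against.** **Total duration recovers the later days.** Stay before first dose is fixed before treatment, so randomization balances it in expectation. If the cap is not carried over, the between-arm difference in total duration estimates the uncapped post-dose difference plus noise, deaths aside. This stands in part: Day 14 onwards is lost from one of the two variables, not both. But 13.1.5 does not say whether the cap and death rules carry over, and the variable has neither the right start nor the right end.

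**Section 15 concerns analyses, and the protocol's analysis paragraph for hospital days names no window.** That is true; the window stands in the endpoint lists. But the SAP repeats it in Sections 4 and 12.1, so it contradicts itself, and the window was not among the matters left to the SAP.

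**A 14-day window is observable for nearly everyone, and scoring deaths at 28 dilutes the comparison.** With medians 7/5, SD 0.5 and 10% deaths in each arm, the standardised effect is 0.49 over 14 days and 0.28 over 28. These are fair reasons to prefer 14 days, but the SAP gives none. Vital status to Day 28 is already needed for all-cause mortality in 13.1.7. Scoring deaths this way extends the SAP's own rule; it is a choice of estimand that should be stated.

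**The numbers rest on assumptions.** They do. The extremes of 69% and 31% need an 18-day median in the longer-stay arm. The scenarios where the 28-day difference vanishes or reverses need 20% deaths in the shorter-stay arm. If that is SIR1-365, 20% of 30 is 6 deaths, above the protocol's enrollment-halt trigger of more than three.

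**Conclusion.** The concern holds. The endpoint and its derivation cover different windows, no planned variable supplies the stated endpoint, and the change is undeclared. That conclusion needs no assumption beyond the text.

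The size depends on unknown stay and death distributions. Within the log-normal scenarios, the 14-day window shows about a third to nine tenths of the 28-day difference when death rates are equal, and can exceed it when the arm with shorter stays has more deaths. No clear power loss is claimed; with deaths scored at the cap, the 14-day version is often the more sensitive one.

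This affects one secondary endpoint in an exploratory phase 1b trial and leaves the primary safety conclusion alone. It should be fixed, but it is not critical.

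**What to change.** In SAP 13.1.5:

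- Derive days hospitalized from first dose (randomization if untreated, as in 13.1.3) through Day 28, maximum 28, summing all readmission intervals in that window.
- Extend the existing death rules consistently: 28 minus days alive and out of hospital before death. An in-hospital death scores 28 − 0 = 28. Discharge after 5 days with death 5 days later scores 28 − 5 = 23, where the present rule gives 14 − 5 = 9. State that days after death count as not discharged.
- State what is assumed about readmissions after last contact when follow-up ends before Day 28.
- Keep the 14-day analysis as supplementary and add a Day 28 table.
- Say whether the cap and death rules apply to total duration.

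If 14 days is to remain the main window, declare and justify it in Section 15.

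The cost is wording, programming and one table, from eCRFs that 13.1.5 already names. The drawback is incomplete late follow-up. A patient discharged and last dosed on Day 5 has the final visit 14 (±3) days later, at about Day 16 to 22, so later readmissions may go unobserved.
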